### **5.3                   Exclusion Criteria**

A participant who meets any of the following criteria will be excluded from the study.

1. Previously participated in a clinical study with mavacamten
2. Hypersensitivity to mavacamten or any of the components of the mavacamten formulation
3. Participated in a clinical trial where the participant received any investigational drug (or is currently using an investigational device) within 30 days prior to Screening or 5 times the respective elimination half-life (whichever is longer)
4. Has a known infiltrative or storage disorder causing cardiac hypertrophy that mimics nHCM, such as Fabry disease, amyloidosis, or Noonan syndrome with LV hypertrophy
5. Has any medical condition that precludes upright exercise stress testing
6. Has a history of syncope or a history of sustained ventricular tachyarrhythmia with exercise within the past 6 months
7. Has a history of resuscitated sudden cardiac arrest at any time or known appropriate implantable cardioverter defibrillator (ICD) discharge within 6 months prior to Screening
8. Has paroxysmal, intermittent atrial fibrillation with atrial fibrillation present per the investigator's evaluation of the participant's electrocardiogram (ECG) at the time of Screening
9. Has persistent or permanent atrial fibrillation not on anticoagulation for at least 4 weeks prior to Screening and/or is not adequately rate-controlled within 6 months prior to

Screening (note: patients with persistent or permanent atrial fibrillation who are anticoagulated and adequately rate-controlled are allowed)

10. Is currently treated with disopyramide or ranolazine (within 14 days prior to Screening) or treatment with disopyramide or ranolazine is planned during the study
11. For participants on beta blocker, verapamil, or diltiazem, any dose adjustment < 14 days before Screening (see [Section 7.7.2](#))
12. Currently treated or planned treatment during the study with a combination of beta blocker and verapamil or a combination of beta blocker and diltiazem
13. Has been treated with invasive septal reduction (surgical myectomy or percutaneous alcohol septal ablation) within 6 months prior to Screening (note: if a participant has had prior septal reduction therapy, the diagnostic wall thickness criteria and all other eligibility criteria must be met at time of Screening)

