### **9.3.4        *Cardiac Monitoring Skin Patch***

At 2 time points during the study, participants will wear a small device to collect HR and rhythm data ([Table 1](#)). The self-contained device attaches to the skin using medical adhesive and contains surface electrodes, internal electronics to capture a continuous single lead ECG waveform, an accelerometer to capture physical activity, sufficient solid state memory to

store data over multiple days, and a battery to power the device. Two sequential patches will be worn for approximately 7 days (14 days total). Following a period of data collection, the device will be transported to a core laboratory where the continuous ECG waveforms and activity record stored on the device will be uploaded for analysis. The analysis will provide full disclosure capabilities for HR, heart rhythm, and physical activity over the period during which the device was properly applied and functioning. The device will be used to explore the pattern of HR and heart rhythm before and during treatment with study drug.

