6.1. Study Endpoints

Safety Endpoints:

- Frequency and severity of treatment-emergent AEs, AEs of special interest, and SAEs
- Frequency of laboratory abnormalities
- Change from baseline vital signs
- Frequency of cardiac rhythm abnormalities

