13.5. Cardiac Rhythm Monitoring (including Holter Monitor)

The summary statistics (including mean, median, SD, minimum and maximum) of atrial fibrillation (AF), nonsustained ventricular tachycardia (NSVT) will be calculated for each visit (baseline and post-baseline time points) and presented by treatment group. For each cardiac event type, the number of subjects with at least one occurrence, the number of episodes per subject per day, and the duration of each episode will also be summarized. Additional parameters may be summarized as appropriate.

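### SAP 13.5 names no AF burden and no per-participant episode duration, so a change from paroxysmal to continuous AF lowers the planned episode rate.

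*SAP*

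**What the plan says.** SAP 2.1 makes safety and tolerability the primary objective, and SAP 6.1 lists "Frequency of cardiac rhythm abnormalities" as one of four safety endpoints. SAP 13.5 says how that endpoint is summarized:

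- "The summary statistics (including mean, median, SD, minimum and maximum) of atrial fibrillation (AF), nonsustained ventricular tachycardia (NSVT) will be calculated for each visit". The AF or NSVT quantity being averaged is not named.
- "For each cardiac event type, the number of subjects with at least one occurrence". This measure takes the participant as the unit.
- A rate and a duration come next: "the number of episodes per subject per day, and the duration of each episode will also be summarized".
- The section closes with an open clause: "Additional parameters may be summarized as appropriate". No further parameter is named.

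The section does not define an episode, say how AF present throughout a recording is counted, or give the time denominator for the daily rate. It also leaves open whether the unit for duration is the episode or the participant.

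Two protocol sections bear on this. In Protocol 5.3, criterion 9 notes that "patients with persistent or permanent atrial fibrillation who are anticoagulated and adequately rate-controlled are allowed", while criterion 8 excludes paroxysmal AF only when AF is present on the Screening ECG. One arm can therefore hold both patterns. Protocol 9.3.4 limits the data to what is recorded "over the period during which the device was properly applied and functioning", and describes wear as "Two sequential patches will be worn for approximately 7 days (14 days total" (the bracket closes there). It does not say whether the 14 days apply to each monitoring period or to both together. Table 1 footnote m places the two periods between Screening and Day 1 and between Weeks 12 and 16.

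**The concern.** An episode rate suits a rhythm that comes in short runs. NSVT does, but AF need not. Once AF is continuous there is nothing left to count after the first onset, so the rate is lowest where AF is most extensive. Each participant has a recording before treatment and one on treatment. The change a reader would most want to see, from paroxysms to continuous AF, appears in the rate as improvement.

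Duration should correct for this. However, if it is summarized episode by episode, the participants with the most episodes carry the most weight, and those may be people with very little time in AF. The risk is a rhythm table in which the rate and the median duration point away from the amount of AF in the arm.

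**Working it through.** **Inputs.** The documents give no rhythm event rates, episode lengths or variability, so there is no planned figure to reproduce. From the documents: about 20 participants per group (SAP 5) and 14 or 7 days of wear per period (Protocol 9.3.4, both readings used). Assumed for illustration: run rates and run lengths, full wear, and AF throughout a recording counted as one episode.

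**Formulas.** Rate = episodes / days worn. Burden = minutes in AF / minutes worn. Fourteen days is 14 × 24 × 60 = 20,160 minutes; 7 days is 10,080.

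**One participant.**

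- AF throughout: 1/14 = 0.071 per day (1/7 = 0.143), burden 100%.
- One 5-minute run a day: rate 1, burden 5/1,440 = 0.35%.
- Ten 2-minute runs a day: rate 10, burden 20/1,440 = 1.4%.
- Four 30-minute runs a day: rate 4, burden 120/1,440 = 8.3%. On moving to continuous AF the rate falls by 1 − 0.071/4 = 98% (1 − 0.143/4 = 96% over 7 days), while burden rises to 100%.

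The direction does not depend on these choices. It holds for any starting rate above one episode per recording.

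**Three hypothetical arms of 20**, at 14 days (7 days in brackets), with durations taken per episode:

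- Arm A: 3 in AF throughout, 2 with a single 30-minute episode, 15 with none.
- Arm B: 2 with ten 2-minute runs a day, 3 with a single 30-minute episode, 15 with none.
- Arm C: 3 in AF throughout, 2 with ten 2-minute runs a day, 15 with none.

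| Summary | Arm A | Arm B | Arm C |
|---|---|---|---|
| Subjects with an occurrence | 5/20 | 5/20 | 5/20 |
| Mean episodes/day | 0.018 (0.036) | 1.011 (1.021) | 1.011 (1.021) |
| Median episodes/day | 0 | 0 | 0 |
| Median duration, min | 20,160 (10,080) | 2 (2) | 2 (2) |
| Mean duration, min | 12,108 (6,060) | 2.3 (2.6) | 215.7 (213.4) |
| Maximum duration, min | 20,160 (10,080) | 30 (30) | 20,160 (10,080) |
| Mean burden | 15.0% (15.0%) | 0.16% (0.18%) | 15.1% (15.1%) |

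- A against B: the mean rate and the burden rank the arms in opposite order.
- B against C: subjects affected, mean rate and median duration are the same, although burden is 0.16% against 15.1%. Only the mean and maximum duration differ.
- A against C: burden is nearly equal, yet mean duration differs by 12,108/215.7 = 56 times, because two participants in C add 280 short runs.
- In B, 2 of 20 participants supply 280 of 283 episodes, 98.9% (140 of 143, 97.9%, over 7 days).

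**The ceiling.** Let one frequent-run participant in Arm C move to continuous AF (14 days). Subjects affected stay at 5/20, maximum duration stays at 20,160 and median duration stays at 2. The mean rate falls to (10 + 4/14)/20 = 0.51. Mean burden rises to (4 × 100 + 1.4)/20 = 20.1%. Mean duration per episode does rise, to (4 × 20,160 + 140 × 2)/144 = 562 minutes, but the A–C comparison shows that its level cannot be read as time in AF.

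**Wear time.** At an assumed 0.1 NSVT runs a day and Poisson occurrence, the chance of at least one run is 1 − exp(−0.1 × T): 75% for T = 14 analyzable days and 50% for T = 7. If the period is 7 days, halving the wear takes it from 50% to 30%. A count of subjects affected is therefore hard to read without the analyzable time beside it.

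**The case against.** The strongest reply is that SAP 13.5 does not rest on the rate alone. The same sentence plans the number of subjects affected, which weights everyone equally, counts a participant in continuous AF, and fits the endpoint's wording most directly. Duration gives continuous AF its longest possible value, and the maximum is among the listed statistics. The median rate is not moved by a few participants with frequent runs. New continuous AF could also appear on the 12-lead ECGs at every onsite visit except Week 6 (Protocol 9.3.3), in the ECG morphology listing (SAP 13.2), or as an adverse event. Burden could be derived later from the stored waveforms.

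Most of this is correct, and it limits the point. A reader might infer that continuous AF would be hidden or reported as event-free. The documents do not support that; the fault lies in the rate and, where short runs dominate, in an episode-level duration summary. A reader might also infer that durations are pooled and treated as independent. SAP 13.5 says neither. It leaves the unit open, and independence would matter only for tests or intervals, which it does not plan. Nor is there any sign that wear will be shorter on treatment or will differ by arm.

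What the reply does not remove: a paroxysmal-to-continuous change is a yes before and a yes after in the count of subjects affected. The maximum cannot rise once one participant in the arm has permanent AF. The median rate was 0 in every arm above and so tells the reader little. The clause allowing additional parameters commits to nothing.

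**Conclusion.** The point holds for AF. The planned rate scores AF throughout a recording at 0.07 per day (0.14 over 7 days) at 100% burden, and falls when frequent paroxysms become continuous. The other planned summaries offset this in part only. That follows from the definition of the rate and from eligibility, given that unbroken AF counts as one episode, which SAP 13.5 does not state either way. The arm-level figures rest on assumed run rates and lengths and show direction, not expected size.

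For NSVT the point is smaller. Runs are short and the plan already expresses them per day, so what remains is the weight of a few participants in an episode-level duration summary and the unstated time denominator.

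SAP 13 plans no hypothesis test on safety variables, so no error rate is affected. What is affected is how the rhythm tables read, and with no test planned those tables are the evidence on this endpoint. This is an inexpensive improvement worth making, not a flaw that invalidates the plan.

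**What to change.** Amend SAP 13.5 as follows.

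- **AF:** add burden per participant (AF time divided by analyzable wear time), by arm and period. State how AF lasting the whole recording is counted. Show participants in AF throughout the baseline recording separately. Reduce episode duration to one value per participant, longest or total.
- **NSVT:** keep the planned episodes per day, with analyzable time as the denominator, and add the longest run per participant.
- **Both:** tabulate analyzable hours by arm and period beside the counts of subjects with at least one occurrence.

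The cost is a few derived variables and table rows. The core laboratory already analyzes the continuous waveforms under Protocol 9.3.4, so no new data, visits or procedures are needed.

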13.6. Other Safety Analyses

Abnormal physical examination results will be listed by subject, and clinical significance. Medical history, concomitant, and prior medications will be summarized in tables and listings.

HCM history, including frequency of SRT (septal reduction therapy) will be summarized in a separate table by treatment and overall.

The number of subjects who met each IMP stopping criteria per protocol will be summarized by treatment and overall.

[REDACTED]

15. INTERIM ANALYSIS

[figure not shown]
[figure not shown]
No interim analysis is planned.

16. SUMMARY OF CHANGES FROM PROTOCOL DEFINED ANALYSES

[figure not shown]
The figure consists of 15 horizontal bars, each composed of a thick black line and a thin white line. The black line starts at the left edge of the frame and extends to a varying position on the right, with the length of the black segment increasing from left to right. The white line is positioned at the far right end of each bar. The bars are evenly spaced vertically.

Biophysical J. 2012;102(3 suppl 1):613a-614a. Available at:

APPENDIX A.

Figure 1: Study Schema

Abbreviations: CPET, cardiopulmonary exercise testing; EOS, end of study; NT-proBNP, N-terminal pro b-type natriuretic peptide; PK, pharmacokinetic blood sample taken; QD, once daily; stress echo, stress echocardiography; TTE, transthoracic echocardiogram.

Table 1: Schedule of Study Procedures

Assessment ^a	Screening ^b Day -28 to Day -1	Day 1	Week 2 (telephone call) ^c	Week 4 ^c	Week 6 ^c	Week 8 ^c	Week 10 (telephone call) ^c	Week 12 ^c	Week 14 (telephone call) ^c	Week 16 ^c /ET	Week 24 ^c /EOS
General Procedures											
Informed consent	X										
Medical history ^d	X										
Vital signs ^e	X	X		X		X		X		X	X
AEs ^d	X	X	X	X	X	X	X	X	X	X	X
ICD information downloaded ^f	X									X	
Prior/concomitant medications	X	X	X	X	X	X	X	X	X	X	X
Physical examination including height and weight ^g	X	X		X		X		X		X	X
ECG ^h	X	X		X		X		X		X	X
Resting TTE ⁱ	X	X		X		X		X		X	X
Post-exercise stress echocardiography ^j	X										
CPET ^k		X								X	
Accelerometer attached ^l	X							X			
Apply cardiac monitoring skin patch ^m	X							X			
Randomization		X									
Laboratory											
Hepatitis panel, HIV test	X										
██████████				X		X		X		X	X
Coagulation panel	X	X		X		X		X		X	X

Table 1: Schedule of Study Procedures (cont'd)

Assessment ^a	Screening ^b Day -28 to Day -1	Day 1	Week 2 (telephone call) ^c	Week 4 ^c	Week 6 ^c	Week 8 ^c	Week 10 (telephone call) ^c	Week 12 ^c	Week 14 (telephone call) ^c	Week 16 ^c /ET	Week 24 ^c /EOS
Laboratory (continued)											
Chemistry	X	X		X		X		X		X	X
Hematology	X	X		X		X		X		X	X
Urinalysis	X	X									X
hs-cardiac troponin I		X		X		X		X		X	X
NT-proBNP ^o	X ^o	X ^o		X		X		X		X ^o	X
TSH	X										
FSH ^p /Serum pregnancy test (women) ^q	X										
Urine pregnancy test (women) ^q		X		X		X		X		X	X
		X									
		X									
		X									
Symptom Assessments											
NYHA class	X	X		X		X		X		X	X
PRO Assessments											
		X								X	X
	X ^v		←	→		X ^w		X ^w	X ^w	X ^w	
	X ^x				X	X		X	X	X	
					X	X		X	X	X	

Footnotes and abbreviations are defined on last page of table.

Table 1: Schedule of Study Procedures (cont'd)

Assessment ^a	Screening ^b Day -28 to Day -1	Day 1	Week 2 ^c (telephone call)	Week 4 ^c	Week 6 ^c	Week 8 ^c	Week 10 (telephone call) ^c	Week 12 ^c	Week 14 (telephone call) ^c	Week 16 ^c /ET	Week 24 ^c /EOS
Investigational Medical Product											
IMP QD			←							→	
IMP administered at site		X								X	
IMP compliance ^y				X	X	X		X		X	

Abbreviations: AE, adverse event; BP, blood pressure; CPET, cardiopulmonary exercise testing; DNA, deoxyribonucleic acid; ECG, electrocardiogram; eCRF, electronic case report form; EOS, end of study; [REDACTED]; ET, early termination; FSH, follicle-stimulating hormone; HCM, hypertrophic cardiomyopathy; [REDACTED] HIV, human immunodeficiency virus; HR, heart rate; hs, high-sensitivity; ICD, implantable cardioverter-defibrillator; ICF, informed consent form; IMP, investigational medicinal product; [REDACTED] LVOT, left ventricular outflow tract; NT-proBNP, N-terminal pro b-type natriuretic peptide; NYHA, New York Heart Association; [REDACTED]; PK, pharmacokinetic; PRO, patient-reported outcomes; QD, once daily; TSH, thyroid-stimulating hormone; TTE, transthoracic echocardiography.

^a Preferred order of assessments is symptom questionnaires; the following 3 assessments in any order: ECG, vital signs, and TTE; pre-exercise blood draws; exercise test; and post-exercise blood draws.

^b Screening may require more than 1 visit to accommodate all of the study procedures.

^c All post-Day 1 study visits have a window of \pm 7 days. At Weeks 2, 10, and 14, patients will be contacted by telephone to collect AE and concomitant medication data.

^d Changes in baseline conditions from once the ICF is signed are recorded on the medical history eCRF unless the change is related to a study procedure, which is then considered an AE. All changes that occur after the administration of the IMP are recorded as AEs.

^e At Screening, ET (if applicable), Week 16 (end of treatment), and Week 24 (end of study), complete vital signs including temperature, HR, respiratory rate, and BP will be obtained. At all other onsite visits except Week 6, only HR and BP are required. If PK sampling is conducted at a visit, vital signs should be collected before PK sampling. Vital signs should be taken with the patient in the same position at all visits. BP should be taken via an automated recorder after the patient rests for at least 5 minutes.

^f For patients who have ICDs, information including rhythm strips and events will be downloaded from the ICDs.

^g At Screening, Week 16, and Week 24, a complete physical examination will be conducted, including a neurological examination. At Week 4, Week 8, and Week 12, an abbreviated cardiopulmonary physical examination will be conducted, with other systems assessed as directed by interval history. Physical examinations will also include height (at Screening only) and weight (at all onsite visits at which a physical examination is performed).

^h 12-lead ECGs will be performed at Screening and all onsite visits except for the Week 6 visit after 10 minutes of rest. Each time an ECG is completed, a 10-second paper ECG will be obtained and maintained in the study patient's source documentation. On Day 1, an ECG will be performed predose.

[figure not shown]
ⁱ Resting TTE should be performed prior to post-exercise stress echocardiography or CPET. Instantaneous peak LVOT gradient at rest and provoked peak LVOT gradient (Valsalva maneuver) will be assessed only at Screening.

[figure not shown]
[figure not shown]
- j After a 4-hour fast, patients will undergo a standard symptom-limited exercise test by standardized treadmill or bicycle ergometer. Instantaneous peak LVOT gradient will be assessed immediately post-exercise by TTE.
- k CPET by standardized treadmill or bicycle ergometer will be performed on both Day 1 and at Week 16/ET prior to dosing. CPET is done after a 4-hour fast. Obtain CPET with study patient in the same position at Week 16 as done on Day 1.
- l The accelerometer is to be distributed during Screening and at the Week 12 visit and retrieved at the Day 1 and Week 16 visits.
- m The cardiac monitoring adhesive skin patch is to be applied during Screening and at the Week 12 visit and retrieved at the Day 1 and Week 16 visits.
- n Blood samples for PK will be collected at all post-Screening onsite visits except for the Day 1 and Week 6 visits. The time of each blood draw will be recorded. At Week 16, a PK sample will be collected before dosing as well as within 2 hours postdose. On other PK sampling days, the PK blood samples can be taken at any time that best facilitates conduct of all scheduled study procedures. The date and time of the last dose of IMP taken prior to the PK sample collection will be recorded.
- o At Screening, the blood draw for NT-proBNP will occur prior to post-exercise stress echocardiography. At the Day 1 and Week 16 visits, the blood draw for NT-proBNP will be obtained both prior to and immediately after CPET.
- p FSH testing at Screening for postmenopausal women to confirm postmenopausal status.
- q Pregnancy testing for all females of childbearing potential. Conduct serum test at Screening and a urine pregnancy test at all other visits shown; conduct serum test if a urine test is positive. At Week 20, a urine pregnancy test will be conducted at home.
- r Separate consent is required for HCM genotyping. Note that if a patient with a prior HCM clinical genotype test that was positive for pathogenic HCM-causing mutation(s) consents to provide their results, then no further genotype assessment will be performed. However, patients who have not been tested, patients who have tested negative for pathogenic HCM-causing mutation(s) on clinical panels, and patients who have a positive HCM genotype result but cannot provide the results or will not consent to provide the results may consent to have blood drawn on Day 1 prior to the first dose of IMP for assessment of HCM genotype.
- s Patients may also consent separately to have blood drawn prior to dosing on Day 1 for assessment of pharmacogenetics and potentially additional DNA sequencing.
- t Patients will have blood samples drawn on Day 1 and Week 16 prior to dosing and at Week 24 for potential exploratory biomarker analysis.

[figure not shown]
- 

[figure not shown]

<img alt="Redacted text" data-bbox="88 8340
